5.1 Overall Design

NOTE: As of Amendment 05, epacadostat and matching placebo are removed from the treatment groups. All participants remaining on study will continue open-label pembrolizumab monotherapy. Participants may choose to discontinue from the study and be treated as per standard of care, or continue on study and receive pembrolizumab monotherapy as per protocol, if they will have access issues to standard of care outside the protocol. The Second Course Phase is removed from the study. The last study visit is the Safety Follow-up Visit and there will be no follow-up for survival status. All imaging will be performed as per local standard of care, data will not be collected or sent for central radiologist review (BICR). This section has been updated accordingly.

This is a Phase 2 randomized, double-blind, active-controlled, parallel-group, multi-site study conducted in participants with metastatic NSCLC who have not previously received systemic therapy for metastatic disease, whose tumors express PD-L1 with a TPS $\geq 50\%$, and in whom EGFR, ALK, or ROS1-directed therapy is not indicated.

The original study design randomized participants into 2 treatment arms: pembrolizumab plus epacadostat and pembrolizumab (open-label) plus matching placebo (see [Figure 1](#)). As of Amendment 05, epacadostat and matching placebo are removed from the study. All participants remaining in the study receive open-label pembrolizumab monotherapy (see [Figure 2](#)).

Randomization into the original treatment arms in the study was stratified by predominant tumor histology (squamous vs. non-squamous).

Participants will be evaluated with radiographic imaging to assess response to treatment as per local standard of care until PD as assessed by the investigator/site radiologist using RECIST 1.1 or initiation of a new anti-cancer regimen.

Adverse event monitoring will be ongoing throughout the study and graded in severity according to the guidelines outlined in the National Cancer Institute Common Terminology Criteria for Adverse Events (NCI CTCAE) v4.0.

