8.1 Discontinuation of Study Treatment

NOTE: As of Amendment 05, this section has been updated. Participants will be discontinued from the study after completing the Safety Follow-up Visit.

Discontinuation of study treatment does not represent withdrawal from the study.

As certain data on clinical events beyond study treatment discontinuation may be important to the study, they must be collected through the participant's last scheduled follow-up, even if the participant has discontinued study treatment. Therefore, all participants who discontinue study treatment prior to completion of the treatment period will still continue to participate in the study as specified in Section 2 and Section 9.9.3.

Participants may discontinue study treatment at any time for any reason or be dropped from the study treatment at the discretion of the investigator should any untoward effect occur. In addition, a participant may be discontinued from study treatment by the investigator or MSD if study treatment is inappropriate, the trial plan is violated, or for administrative and/or other safety reasons. Specific details regarding procedures to be performed at study treatment discontinuation are provided in Section 9.1.10.

A participant must be discontinued from study treatment but continue to be monitored in the study for any of the following reasons:

- The participant or participant's legally acceptable representative requests to discontinue study treatment.
- Radiographic disease progression as assessed by the investigator per RECIST 1.1, as outlined in Section 9.2.1 (except if MSD approves treatment continuation).
- Unacceptable adverse experiences as described in Section 7.2.1.
- The participant interrupts study treatment administration for more than 12 consecutive weeks, unless approved with written documentation from MSD.
- The participant has a medical condition or personal circumstance which, in the opinion of the Investigator and/or MSD, placed the participant at unnecessary risk from continued administration of study treatment.
- The participant has a confirmed positive serum pregnancy test.
- Noncompliance with study treatment or procedure requirements.
- Any progression or recurrence of any malignancy, or any occurrence of another malignancy that requires active systemic treatment.
- Completion of 35 treatment administrations (approximately 2 years) with pembrolizumab.

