9.2 Efficacy Assessments

9.2.1 Tumor Imaging and Assessment of Disease

NOTE: As of Amendment 05, central review of imaging (BICR) and iRECIST are no longer applicable. Disease assessments will be performed by the site investigator/radiology assessment per local standard of care. This section has been updated accordingly.

Tumor imaging is strongly preferred to be acquired by CT. For the abdomen and pelvis, contrast-enhanced magnetic resonance imaging (MRI) may be used when CT with iodinated contrast is contraindicated or when local practice mandates it. MRI is the strongly preferred modality for imaging the brain. The same imaging technique regarding modality (ideally the same scanner) and the use of contrast should be used in a participant throughout the study to optimize the reproducibility of the assessment of existing and new tumor burden and improve the accuracy of the assessment of response or progression based on imaging.

Participant eligibility will be determined using local assessment (Investigator assessment) based on RECIST 1.1.

Treatment should continue until PD has been determined by investigator-assessed disease progression by RECIST 1.1; no confirmatory scans are required. However, if the participant is achieving a clinically meaningful benefit, an exception to continue with pembrolizumab monotherapy may be considered following consultation with the MSD.

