9.3 Adverse Events, Serious Adverse Events and Other Reportable Safety Events

The definitions of an adverse event (AE) or serious adverse event (SAE), as well as the method of recording, evaluating, and assessing causality of AE and SAE and the procedures for completing and transmitting AE, SAE and other reportable safety event reports can be found in Appendix 4.

Progression of the cancer under study is not considered an adverse event as described in Section 9.3.5 – Disease-Related Events and/or Disease-Related Outcomes Not Qualifying as AEs or SAEs, and Appendix 4.

AE, SAEs, and other reportable safety events will be reported by the participant (or, when appropriate, by a caregiver, surrogate, or the participant's legally authorized representative).

The investigator, who is a qualified physician, and any designees are responsible for detecting, assessing, documenting, and reporting events that meet the definition of an AE or SAE as well as other reportable safety events. Investigators remain responsible for following up AE, SAEs and other reportable safety events for outcome according to Section 9.3.3.

Adverse events will not be collected for participants during the pre-screening period (for determination of archival tissue status) as long as that participant has not undergone any protocol-specified procedure or intervention. If the participant requires a blood draw, fresh tumor biopsy etc., the participant is first required to provide consent to the main study and AEs will be captured according to guidelines for standard AE reporting.

9.3.1 Time Period and Frequency for Collecting AE, SAE and Other Reportable Safety Event Information

All AEs, SAEs and other reportable safety events that occur after the consent form is signed but before treatment allocation/randomization must be reported by the investigator if the participant is receiving placebo run-in or other run-in treatment, if the event cause the participant to be excluded from the study, or is the result of a protocol-specified intervention, including but not limited to washout or discontinuation of usual therapy, diet, or a procedure.

- All AEs from the time of treatment allocation/randomization through 30 days following cessation of study treatment must be reported by the investigator.

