- All AEs meeting serious criteria, from the time of treatment allocation/randomization through 90 days following cessation of study treatment, or 30 days following cessation of study treatment if the participant initiates new anticancer therapy, whichever is earlier must be reported by the investigator.
- All pregnancies and exposure during breastfeeding, from the time of treatment allocation/randomization through 120 days following cessation of study treatment, or 30 days following cessation of study treatment if the participant initiates new anticancer therapy must be reported by the investigator.
- Additionally, any SAE brought to the attention of an investigator at any time outside of the time period specified above must be reported immediately to the Sponsor if the event is considered to be drug-related.

Investigators are not obligated to actively seek AE or SAE or other reportable safety events in former study participants. However, if the investigator learns of any SAE, including a death, at any time after a participant has been discharged from the study, and he/she considers the event to be reasonably related to the study treatment or study participation, the investigator must promptly notify MSD.

All initial and follow-up AEs, SAEs and other reportable safety events will be recorded and reported to MSD or designee within the timeframes as indicated in [Table 6](#).

Table 6 Reporting Time Periods and Timeframes for Adverse Events and Other Reportable Safety Events

Type of Event	Reporting Time Period: Consent to Randomization/ Allocation	Reporting Time Period: Randomization/ Allocation through Protocol-Specified Follow-up Period	Reporting Time Period: After the Protocol Specified Follow-up Period	Timeframe to Report Event and Follow-up Information to MSD:
Non-Serious Adverse Event (NSAE)	Report if: - due to protocol-specified intervention - causes exclusion - subject is receiving placebo run-in or other run-in treatment	Report all	Not required	Per data entry guidelines
Serious Adverse Event (SAE) including Cancer and Overdose	Report if: - due to protocol-specified intervention - causes exclusion - subject is receiving placebo run-in or other run-in treatment	Report all	Report if: - drug/vaccine related. (Follow ongoing to outcome)	Within 24 hours of learning of event

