10.6.2 Statistical Methods for Safety Analyses

As of Amendment 05, safety and tolerability will be assessed by clinical review of all relevant parameters including adverse experiences (AEs), laboratory tests, and vital signs.

Individual events and the broad AE categories consisting of the proportion of participants with any AE, a drug-related AE, a serious AE, an AE which is both drug-related and serious, a Grade 3-5 AE, a drug related Grade 3-5 AE, a fatal AE, dose interruption due to an AE and discontinuation due to an AE, will be summarized by counts and percentages by treatment group (Table 13).

Table 13 Analysis Strategy for Safety Endpoints

Safety Endpoint	Descriptive Statistics
Any AE	X
Any Serious AE	X
Any Grade 3-5 AE	X
Any Drug-Related AE	X
Any Serious and Drug-Related AE	X
Any Grade 3-5 and Drug-Related AE	X
Dose Interruption due to AE	X
Discontinuation due to AE	X
Death	X
Specific AEs, SOCs	X
Change from Baseline Results (Laboratory toxicity grade)	X

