10.9 Sample Size and Power Calculations

10.9.1 Sample Size and Power for Efficacy Analyses

The study will randomize 148 participants in a 1:1 ratio into the pembrolizumab plus epacadostat and pembrolizumab plus placebo arms. ORR is a primary endpoint for the study and PFS and OS are secondary endpoints.

[Figure 3](#) summarizes power calculations for the primary hypothesis under various ORR difference assumptions.

[figure not shown]

Figure 3 Power for Primary Hypothesis under Different Effect Size Assumptions

Based on the 148 participants in the control arm and the treatment arm under comparison, the power of the ORR testing at the $\alpha=0.05$ (one-sided) is approximately 81.7% to detect a difference of 20 percentage points in ORR between an underlying 50% response rate in the control arm and a 70% response rate in the experimental arm.

With 95 PFS events, the study will have 80% power to detect a hazard ratio of 0.6 at an alpha level of 5% (1-sided).

The sample size and power calculations were performed in R (package “gsDesign”).

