### 3.6.3 Statistical Methods for Safety Analyses

Safety and tolerability will be assessed by clinical review of all relevant parameters including AEs, laboratory tests, vital signs, and ECG measurements.

The analysis of safety results will follow a tiered approach (Table 5). The tiers differ with respect to the analyses that will be performed. Safety parameters or AEs of special interest (AEOSI) that are identified a priori constitute "Tier 1" safety endpoints that will be subject to inferential testing for statistical significance with p-values and 95% CIs provided for between-group comparisons. Other safety parameters will be considered Tier 2 or Tier 3. Tier 2 parameters will be assessed via point estimates with 95% CIs provided for between-group comparisons; only point estimates by treatment group are provided for Tier 3 safety parameters.

AEOSI that are immune-mediated or potentially immune-mediated are well documented and will be evaluated separately; however, these events have been characterized consistently throughout the pembrolizumab clinical development program and determination of statistical significance is not expected to add value to the safety evaluation. Similarly, the combination of pembrolizumab and epacadostat has not been associated with any new safety signals. Finally, there are no known AEs associated with participants with NSCLC for which determination of a p-value is expected to impact the safety assessment. Therefore, there are no Tier 1 events expected in this study.

Adverse experiences (specific terms as well as system organ class terms) that are not pre-specified as Tier-1 endpoints will be classified as belonging to "Tier 2" or "Tier 3", based on the number of events observed and clinical interest. For Tier 2 events, 95% CIs will be provided for between-treatment differences in the percentage of participants with events; these analyses will be performed using the Miettinen and Nurminen method.

Because many 95% CIs may be provided without adjustment for multiplicity, the CIs should be regarded as a helpful descriptive measure to be used in review, not a formal method for assessing the statistical significance of the between-group differences in AEs and predefined limits of change.

[figure not shown]

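### AEs are compared between arms only as crude percentages although observation time follows treatment duration; a supplementary exposure-adjusted rate should be added

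*Protocol*

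**What the plan says.** **Analysis.** Under Protocol 10.6.2, individual events and the broad AE categories "will be summarized by counts and percentages by treatment group (Table 13"). Table 13 has one column, descriptive statistics. The sSAP (Section 3.6.3, Table 5), written for Amendment 04, goes further for Tier 2 events: "95% CIs will be provided for between-treatment differences in the percentage of participants with events", by the Miettinen and Nurminen method. Neither document visibly plans a person-time rate, a time to first AE or a cumulative incidence.

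**Observation window.** Protocol 9.3.1: "All AEs from the time of treatment allocation/randomization through 30 days following cessation of study treatment must be reported by the investigator". For serious events the window runs "through 90 days following cessation of study treatment", or 30 days if new anticancer therapy starts.

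**Treatment duration.** Protocol 9.2.1: "Treatment should continue until PD has been determined by investigator-assessed disease progression by RECIST 1.1". Section 8.1 also ends treatment for unacceptable toxicity and at "Completion of 35 treatment administrations (approximately 2 years) with pembrolizumab".

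**Design effect.** Protocol 10.9.1: "With 95 PFS events, the study will have 80% power to detect a hazard ratio of 0.6", one-sided 5%.

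**Exposure.** Protocol 10.12 and sSAP 3.12 summarize the number of cycles in the APaT population, as a separate table not linked to the AE analyses.

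**The concern.** A crude percentage counts a participant with at least one event and ignores how long that participant was watched. Here the length of observation is treatment time plus a fixed tail, and treatment time depends on progression. If one arm stays on treatment longer, it collects more first events even when the event rate per month is the same. The Tier 2 intervals are then centred on a difference that mixes rate with duration, and their width gives no sign of it.

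Safety and tolerability of the two regimens is a secondary objective, so the between-arm reading matters. The link to the plan's own assumptions is indirect. No section states that treatment duration should differ by arm. It follows only from combining treatment to progression with the PFS hazard ratio of 0.6 used for power.

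**Working it through.** **1. The plan's figure.** Power for PFS = Φ(√95/2 × |ln 0.6| − 1.645) = Φ(4.873 × 0.5108 − 1.645) = Φ(0.845) = 80.1%. The stated 80% reproduces.

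**2. Inputs from the documents**
- Control median PFS 10.3 months, lower 95% limit 6.7, from the earlier phase 3 trial in Protocol 3.1 (the SAP states no median).
- AE tail w = 30 days = 0.99 month.
- Treatment cap 35 × 21 days = 735 days = 24.1 months.
- Enrollment ended 05-SEP-2018 and the cutoff was 10-JAN-2019: 127 days, or 18.1 weeks, or 4.2 months. This matches the stated 18-week minimum.
- 74 participants per arm.

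**3. Assumptions not in the documents**
- Exponential time to progression, and treatment stopping only at progression or the cap.
- Constant AE hazard h, the same in both arms.
- Uniform accrual over 8 months, so follow-up is 4.2 to 12.2 months at the cutoff.

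**4. Formulas.** λ = ln 2/10.3 = 0.0673 per month in control, and 0.6 × 0.0673 = 0.0404 in the combination arm. Let D be the longest treatment time that can be observed: 24.1 months at full length, or follow-up minus w at the cutoff, averaged over 4.2 to 12.2 months.
- Mean time at risk = w + (1 − e^(−λD))/λ.
- Crude incidence = 1 − e^(−hw) × [λ/(λ+h) × (1 − e^(−(λ+h)D)) + e^(−(λ+h)D)].
- h is solved so that control incidence is 20% or 40%, then used unchanged in the other arm.

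Full-length time at risk: control 0.99 + (1 − 0.197)/0.0673 = 12.9 months; combination 0.99 + (1 − 0.377)/0.0404 = 16.4 months.

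**5. Results (true AE rate ratio 1.00 throughout)**

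| Setting | PFS HR | Mean months at risk, control vs combination | Control 20% reads | Control 40% reads |
|---|---|---|---|---|
| Cutoff 10-JAN-2019 | 0.6 | 6.6 vs 7.1 | 21.6% (+1.6) | 42.8% (+2.8) |
| Cutoff 10-JAN-2019 | 0.8 | 6.6 vs 6.9 | +0.8 | +1.4 |
| Any | 1.0 | equal | 0 | 0 |
| All through 35 cycles | 0.6 | 12.9 vs 16.4 | 24.8% (+4.8) | 48.2% (+8.2) |

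**6. Range.** I varied the control median from 6.7 to 10.3 months, the AE hazard from 0.01 to 0.10 per month, and the follow-up up to its widest possible span (from the initial protocol date, 06-JUN-2017). With HR 0.6 the gap is about 0.5 to 6 points at the cutoff and 3 to 11 points at full length.

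**7. Sampling error.** The 95% half-width of the difference is 1.96 × √(0.20×0.80/74 + 0.216×0.784/74) = 13.1 points at 20%, and 1.96 × √(0.40×0.60/74 + 0.428×0.572/74) = 15.9 points at 40%.

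**8. Check on the remedy.** Suppose the AE hazard is 0.15 per month for the first 3 months only, equal in both arms, with HR 0.6. Crude percentages are then nearly equal, at about 35% in each arm. The exposure-adjusted rate ratio is 0.94 at the cutoff and about 0.8 at full length. For early-onset events the rate, not the percentage, misleads.

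**The case against.** **The difference in duration is only hypothetical.** The hazard ratio of 0.6 is the alternative for a secondary endpoint. ORR was missed, no PFS result is given, and at a ratio of 1.0 there is no bias. This stands. A reader might infer that the design expects unequal treatment time, but no section says so. Nor does the freedom to leave after Amendment 05 ("Participants may choose to discontinue from the study and be treated as per standard of care") imply an imbalance, since it applies to both arms.

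**The effect is small where the randomized comparison was made.** This also stands. Nobody could have had 24 months of treatment by January 2019, and the gap lies well inside sampling error. Full length is reached only after both arms had moved to pembrolizumab alone, so carrying 0.6 that far is an upper scenario. Even so, the gap is a shift in the estimate, which the interval width does not reveal.

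**Crude tables might hide real harm.** A reader might infer that a 30% higher AE rate could vanish if combination participants stopped 1.5 times as fast. In this model that happens only at full length (19.9% vs 20%, 39.4% vs 40%). With observation cut at 9 months the excess remains visible (22.6% vs 20%, 43.8% vs 40%). The documents give no evidence of faster stopping.

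**Rates have their own flaw.** They assume a roughly constant hazard, and Protocol 7.2.1 says immune-related events may come soon after the first dose or months after the last. Step 8 shows the consequence. This rules out making rates the main basis for safety statements.

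**The documents already help.** The exposure summary would reveal an imbalance, Table 13 is descriptive, and the sSAP calls its Tier 2 intervals descriptive. True, but none of this adjusts the comparison.

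**Conclusion.** The point holds as a modest gap in the safety analysis. Both documents compare AEs between arms only as crude percentages, while observation time follows treatment duration. Under the design hazard ratio of 0.6 and equal constant AE rates, the spurious excess on the combination is about 1.6 to 2.8 points at the January 2019 cutoff, and about 5 to 8 points only if that ratio persisted through 35 cycles. It roughly halves at 0.8 and is zero at 1.0. The actual imbalance is unknown. These sizes rest on exponential progression, treatment stopping at progression or the cap, a 10.3-month control median and an assumed 8-month accrual.

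The documents do not support saying that the safety tables are invalid, that harm has been hidden, or that rates should replace the percentages. They support a supplementary rate.

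**What to change.** In Protocol 10.6.2/Table 13 and sSAP 3.6.3/Table 5:

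- Keep the crude percentages and the Tier 2 intervals.
- Add, as a supplementary descriptive column for the broad AE categories and Tier 2 terms, participants with a first event per 100 person-months by arm, with the rate ratio and its 95% CI.
- End person-time at the first event or at the end of the reporting window for that row, truncated at data cutoff. The window is 30 days after last dose for non-serious AEs. For serious AEs it is 90 days, or 30 days if new anticancer therapy starts. A single 30-day limit would leave SAEs from days 31 to 90 without matching person-time.
- For rows that mix serious and non-serious events, count both events and person-time over a common 30-day window.
- In study-completion tables, split events and person-time at the Amendment 05 switch to pembrolizumab alone.
- State that the rate assumes a roughly constant hazard, can mislead for early-onset events, and is read with the percentages rather than in place of them as the basis for safety statements.

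The cost is some sSAP wording and an extra column from dates already collected. The final analysis is complete and unblinded, so the addition there must be labelled post hoc. For the study-completion tables it can be specified beforehand.
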